3. OBJECTIVES AND ENDPOINTS

OBJECTIVES	OUTCOME MEASURES	JUSTIFICATION FOR ENDPOINTS
Primary		
Feasibility of MCT-KD x three weeks	Composite outcome (all of the following measures must be met):	MCT-KD has never been studied in PD population (expected to

Abbreviated Title: Tolerability and efficacy of ketogenic diet in Parkinson's Disease**Version Date:** 04/19/2021

	
1) Recruitment reaches target of 32 participants or as per pre-set interim analysis
 
2) Study retention rate >80% of all participants at 3 weeks
 
3) Adherence ($\leq 10\%$ mean daily energy from net carb over 2 weeks MCT-KD outpatient, assessed by 2x/week unscheduled phone calls by CC Nutrition staff)
 
4) Acceptability – Likert scale ≥ 2 (at least somewhat likely to use diet in future and at least somewhat effective in improving PD symptoms) at end of study (week 3)
	augment ketosis) and feasibility has not been established.
Secondary		
Timed Up & Go (TUG) time, mean difference between groups on study day 7	Mobility on the Timed Up and Go (TUG) test, daily (fastest of three trials per session) units: seconds Range: 8-18s	TUG time is generally regarded as an index of fall risk – estimated 20% risk reduction with 4s faster time (Nocera et al, 2013)
Tertiary/Exploratory		

Nutritional ketosis (NK) improves PD symptomatology at three weeks in the following: in cognition (improved attention, recall, and executive function), and motor function (reduced akinesia and tremor). A low fat (standard American) diet (SAD) does not.
 
NK reduces non-motor symptoms, subjective motor fluctuations and daily off time within the immediate keto-induction period, while SAD does not (mean difference at 1
	
Stroop word-color interference latency (unit: ms, range: 110-135 ms), 0,1,2,3 back recall task (unit i: % error of missing true n-back letter presented; range i: 0-back 0-10%, 1-back 4-20%, 2-back 15-30%, 3-back 20-32%; unit ii reaction time (RT) ms, range ii 0-back 500-740 ms; 1-back 600-980 ms; 2-back 700-1200 ms; 3-back 700-1200 ms); fingertap speed and rhythm (MN and PQ keyboard tasks; units MN and PQ keystroke speed, in keys/s; range MN
	
All of these tests have been shown to be impaired in PD cohorts and are at least semi-quantitative and amenable to serially repeated measures with good test-retest reliability
 
Scalp EEG is non-invasive, easy to perform in the setting of intervention, and as

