At pre-determined scheduled time as per Exploratory Outcome heading, from 40 stimuli, colored (red, green, blue, yellow) number words will be displayed on a computer screen, and the difference in latencies between incongruent (color and word of the color different) congruent (color and word of the color same) time to correct response will be recorded, a minimum of 20 correct responses. The % correct from total responses will also be recorded. Following is URL to perform the test:

https://www.psytoolkit.org/lessons/experiment_stroop.html

As explained in the software instructions, the fixation in PsyToolkit occurs for 200 ms, and then the colorword trial is shown for 2s - the program records correct and incorrect (or no keystroke) responses separately and averages the latencies over 40 trials.

Testing will occur daily.

Stroop word-color interference is to be tested on day 1, week 3 final visit, and daily on the same testing schedule as a function of the intervention over 7 days.

N-back task

As per pre-determined scheduled time, 3-back task will be tested at a certain time daily with letters A,B,C,D,E,H,I,K,L,M,O,P,R,S,T presented for maximum 2000 ms, at a rate of new stimulus ever 2500 ms, for 20 trials.

If the stimulus is the same as 3 trials ago, participants press the 'M' key. If the stimulus is not the same as 3 trials ago, participants press the 'N' key. (M for memory, N for No)

At the end of 20 trials, error % is given for missing 3-back items, and reaction time (ms) is calculated.

A demo of the test is found here:

https://www.psytoolkit.org/experiment-library/experiment_nback.html

Testing will occur daily and at week 3.

MN and PQ keyboard tasks

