8.2 EFFICACY ASSESSMENTS

As one of the study aims is to determine feasibility of MCT supplemented ketogenic diet, the efficacy of primary objective of study feasibility as per recruitment, retention, acceptability, and adherence will be determined by a composite outcome, in which all criteria are met: completion rate of both inpatient 1 week and outpatient 2 week segments, with target of >80% for each; recruitment target of 32 participants reached; adherence to outpatient diet with mean daily carb $\leq 10\%$; intervention is acceptable to all participants by Likert scale $\geq 2/4$ of likelihood of using this therapy in the future and effectiveness in symptom reduction.

Efficacy of secondary objective of TUG reduction will be assessed by between-group mean difference at 7 days (MCT-KD vs. SAD). It is presumed that the standard (control) diet will not provide any issues of feasibility. Refer to Section 4.1 Study Design for direct and indirect determinations of ketosis.

Timed Up & Go (TUG)

Efficacy of TUG will also factor effect of time, via repeated measures ANOVA for TUG that will be tested three times per session and fastest time used, with same timing relation to dopaminergic medications.

Efficacy will be tested further in the between group difference between the two diets on outcomes of the following, again with same timing regarding dopaminergic medications:

Exploratory measures will be done as per test schedule in Section 4.1, generally once daily or less.

Stroop Word-Color Interference

this test has been shown to be impaired in PD as part of the executive network of actively choosing the stimulus while inhibiting the background. The latency will be determined from a computer test.

N-Back Task (% correct)

This test (Kirchner, 1958) involves a series of visual stimuli such as letters, and then participants are asked if each stimulus matches a stimulus n trials before. Performance is shown to be impaired in PD to a greater degree than in normal aging

Simple Reaction Time (SRT)

SRT (same cue on computer screen, press button; machine is used already for Chronic Fatigue Syndrome protocol studies and will be made available for the study). PD is consistently shown to have increased latency that is attributed to the akinesia as cardinal motor symptom. The increase in latency is reduced by

Abbreviated Title: Tolerability and efficacy of ketogenic diet in Parkinson's Disease

Version Date: 04/19/2021

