1 STATISTICAL CONSIDERATIONS

9.1 STATISTICAL HYPOTHESIS

Primary hypothesis:

Nutritional ketosis supplemented by MCT oil is feasible within a Parkinson Disease cohort as defined by an acceptable retention rate and outpatient adherence.

Primary outcome: Feasibility of nutritional ketosis(ketogenic diet with 80% lipid including MCT oil, 10-15% protein, 5-10% carbohydrate), in Parkinson Disease cohort defined as a composite outcome meeting all of the following criteria: recruitment target of 32 or as per interim power analysis defined in Section 9.4.6; retention rate > 80% at study end; adherence to ketogenic diet in the outpatient portion defined as mean carbohydrate energy intake <10%, and intervention is acceptable to all participants by Likert scale \geq 2/4 of likelihood of using this therapy in the future and effectiveness in symptom reduction, from all study participants at 3 weeks.

Secondary hypothesis:

Abbreviated Title: Tolerability and efficacy of ketogenic diet in Parkinson's Disease

Version Date: 04/19/2021

Nutritional induced ketosis (NK) increases mobility based on TUG score in a Parkinson Disease cohort at 7 days compared to usual diet (35% lipid, 10-15% protein, 50-55% carbohydrate). Secondary outcome: timed Up & Go test (TUG score) at study day 7 (fastest of three trials)

$H_0: \mu_1 = \mu_2$, where μ_1 and μ_2 are the population means for the NK diet group and usual diet group respectively vs. $H_1: \mu_1 \neq \mu_2$.

Exploratory hypotheses:

Hypothesis A: Nutritional ketosis improves PD symptomatology in cognition (improved attention, recall, and executive function, and motor function akinesia and tremor within six days, as assessed by: Stroop word-color interference latency (executive function), n-back recall task (attention and working memory), simple reaction time (akinesia); fingertap speed and rhythm MN and PQ keyboard tasks (fine motor), and autonomic function (heart rate variability at rest and with deep breathing / Valsalva Maneuver tests)

Hypothesis B: The mechanism of symptomatic reduction of NK in PD is both augmented mitochondrial metabolism (direct, rapid) and augmented neurotransmitter and growth factor synthesis (indirect, delayed), especially GABA and dopamine, as assessed by resting state EEG spectral power, phase coherence, and M1 waveform normalization. Accordingly, effect sizes for exploratory outcomes will be greater at 3 weeks than 7 days.

Exploratory outcomes daily (days 1-7), week 3

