9.4.3 Analysis of the Exploratory Outcomes

ANCOVA will be also used to examine the diet effect on the other exploratory outcomes, where each outcome measure over time will be used as a dependent variable with age and the outcome at day 1 as covariates.

Longitudinal analysis methods, such as repeated measures ANCOVA, random coefficient model or mixed model, will be used to examine the change in the exploratory outcomes over the six days. Within-subject

Abbreviated Title: Tolerability and efficacy of ketogenic diet in Parkinson's Disease

Version Date: 04/19/2021

(mixed model) and across-subject (spearman or Pearson) correlation analysis will be applied to evaluate the relationship between outcome variables.

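### The exploratory 3-back score has no single definition, and the miss-only version lets a shift towards pressing M read as better memory

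*Combined protocol and SAP*

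**What the plan says.** The N-back paragraph of section 4.1 makes every trial a two-choice response. For targets: "If the stimulus is the same as 3 trials ago, participants press the 'M' key". For all other letters: "If the stimulus is not the same as 3 trials ago, participants press the 'N' key". Letters come "at a rate of new stimulus ever 2500 ms, for 20 trials". The score is then stated as: "At the end of 20 trials, error % is given for missing 3-back items, and reaction time (ms) is calculated".

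The endpoint table in section 3 gives the unit as the percent "error of missing true n-back letter presented", with reaction time as a second unit. Section 8.2 heads the same test "N-Back Task (% correct" and does not say what the percentage is taken over.

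Section 9.1 uses the "n-back recall task (attention and working memory" as an exploratory outcome and predicts more accurate and faster cognitive performance. Section 9.4.3 says that "ANCOVA will be also used to examine the diet effect on the other exploratory outcomes", with age and the day 1 value as covariates, but does not name the n-back score that enters the model. No section mentions a false-alarm rate, d' or any other score that allows for response bias.

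**The concern.** In a task with targets and non-targets there are two kinds of error: missing a target and pressing M for a non-target. A score built only on the first mixes memory with willingness to press M. Someone who becomes more impulsive, more alert, or simply adopts a different strategy over the eight sessions (days 1 to 7 and week 3) can lower the miss rate without remembering more.

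At stake is the reading of the trial's attention and working-memory outcome. The plan expects improvement on it, and a change in response style could supply an apparent one. Two differently labelled scores, with neither named in the analysis section, also leave room to choose between them after the data are seen.

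**Working it through.** The plan gives no power, effect size or target count for the n-back, so there is no figure of its own to reproduce.

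**Inputs from the protocol.** There are 20 trials per run (section 4.1). The first three have no letter three back, so at most 20 - 3 = 17 trials (4 to 20) can be scored as target or non-target. The section 3 range for 3-back error is 20-32%.

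**Assumptions.** Equal-variance signal-detection model; d' = 1.5; 6 targets and 11 non-targets among the 17 trials; in the second check, false-alarm rates of 5-20%.

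**Boundary case.** Miss % = missed targets / targets. Pressing M on every trial misses none, so error is 0% for any number of targets. Hit rate minus false-alarm rate for the same person is 100% - 100% = 0. Accuracy over the 17 trials would be 6/17 = 35.3%.

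**Criterion shift with memory held fixed.** Hit = Φ(d'/2 - c); false alarm = Φ(-d'/2 - c).

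| | c = +0.25 | c = -0.25 |
|---|---|---|
| Hit | Φ(0.50) = 69.1% | Φ(1.00) = 84.1% |
| Miss | 30.9% | 15.9% |
| False alarm | Φ(-1.00) = 15.9% | Φ(-0.50) = 30.9% |
| Total error, (6 × miss + 11 × false alarm)/17 | 21.2% | 25.6% |
| Hit minus false alarm | 53.2 points | 53.2 points |

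The miss-only score reports error roughly halved. Total error rises, and memory is unchanged by construction.

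**Starting from the section 3 range.** The same 0.5 SD shift, again with d' fixed:

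| Misses | Fall in misses | False alarms (assumed start) | Hit minus false alarm |
|---|---|---|---|
| 20% to 9.0% | 11.0 points | 5% to 12.6% | 75.0 to 78.4 |
| 26% to 12.6% | 13.4 points | 10% to 21.7% | 64.0 to 65.7 |
| 32% to 16.7% | 15.3 points | 20% to 36.6% | 48.0 to 46.7 |

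A 0.25 SD shift takes misses from 20% to 13.7%, or from 32% to 23.6%.

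Hit minus false alarm is not perfectly immune. Pairing each starting miss rate with each of the three false-alarm rates, it moves between -5.6 points (60.0 to 54.4, from 20% misses and 20% false alarms) and +7.7 points (63.0 to 70.7, from 32% and 5%). That is still less than the 11.0 to 15.3 point fall in misses. Under this model d' does not move at all.

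**The case against.** The strongest reply is that the analysed score may not be the miss rate. If percent correct in section 8.2 means accuracy over all trials, false alarms count and the always-M responder does badly. The sentence in 4.1 could also describe the program's end-of-run feedback. This stands in part: a reader might infer that the trial will certainly analyse a miss-only score, and the documents do not settle that. But percent correct could equally be 100 minus the miss rate, and the endpoint table in section 3 names missed targets as the unit.

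Second, randomisation and participant blinding protect the day 7 comparison. A shift shared by both arms, including practice, cancels in expectation; section 4.2 recognises learning on the 3-back and relies on randomisation for it. This stands. To bias that contrast, the diet itself would have to change response style, and no document shows that it does. The protection does not extend to the within-group pre/post comparisons or to week 3, when both groups are on the ketogenic diet. Practice confounds those for any score, d' included, so the fix removes the response-style part only.

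Third, always pressing M goes against the instructions, and d', the size of the shift and the target count are assumed. This is fair: the figures illustrate a mechanism and do not forecast its size.

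Two stronger readings should be resisted:

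- Because the synopsis lists cognition under the secondary objective, a reader might infer that a secondary result is at risk. The only secondary outcome is TUG, and section 3 places cognition under tertiary/exploratory.
- A reader might infer that the score is too coarse for the stated 20-32% range. With 6 targets the nearest attainable scores are indeed 16.7% and 33.3%. But 4 or 8 targets allow 25%, 5 allow 20%, and 7 allow 28.6%. The target count is not given, and section 3 does not say that the range refers to one person's single session.

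**Conclusion.** The point holds for an exploratory outcome. Sections 3 and 4.1 describe a miss rate, 8.2 gives an undefined percent correct, and section 9 does not choose between them. If the miss rate is used, a 0.5 SD move towards M at fixed memory lowers error by 15.0 points in the d' = 1.5 example (30.9% to 15.9%). It lowers error by 11.0 to 15.3 points from starting values in the section 3 range, which is itself 12 points wide.

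These sizes rest on the equal-variance model and the assumed shift. The miss figures do not depend on the number of targets; the total-error figures do. The exposure is mainly in the pre/post and week 3 comparisons. The primary feasibility outcome, the TUG analysis and the sample size are untouched. It is worth correcting because the change is cheap.

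**What to change.** In sections 3, 4.1 and 8.2, define one 3-back accuracy score: hit rate minus false-alarm rate, or d' with a standard correction for rates of 0 and 1, computed over trials 4 to 20. Name that score in section 9.4.3. Report the miss rate and the false-alarm rate beside it. Restricting to trials 4 to 20 matters for the false-alarm rate; a miss rate already excludes the first three trials, since they cannot be targets.

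Before relying on this, confirm that the software saves the M or N response trial by trial. Section 4.1 says that correct and incorrect responses are recorded separately for the Stroop test, but does not say so for the n-back.

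If the responses are saved, this is a change of scoring only, with no new procedure or visit. The cost is slightly less direct comparison with published miss rates, which can still be reported.

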Ketosis values in the MCT-KD group will be correlated indirectly with respiratory quotient and continuous glucose monitor (Freestyle Libre Pro Glucose Monitoring System, continuous glucose monitoring (CGM) system, FDA approved for blinded professional use in clinics). The hypothesis is that nutritional ketosis will improve mobility and also motor and non-motor symptoms through a direct, homeostatic return of frontostriatal signaling by mitochondrial restoration that will occur within hours of reaching ketosis on inpatient day 3, and through an indirect mechanism of increased dopamine / GABA availability (reduction in pathologic glutamatergic hyperexcitability) that will develop more gradually, over several days.

Care will be taken to reduce bias through blinding rater(s) to intervention group ketogenic or non-ketogenic and by blinding participants to intervention or control diet given, with randomization scheme kept only by a study investigator not involved in any of the ratings or measurements (study biostatistician) and by using video rating (aside from muscle tone) of UPDRS-III by the average of AI and another movement disorders specialist outside the study, the latter rating scrambled in random assortment with respect to intervention day. Study duration will be three weeks, and total time for participants approximately four weeks including initial study visit and period of at least one week baseline prospective diet, activity and ON/OFF PD symptom fluctuations self-report, and for baseline diet collection also using unscheduled twice weekly phone calls by study nutritionist / investigator (non-rater). By the time of discharge, participants will receive daily suggested ketogenic diet meal plans for the upcoming two weeks of diet at home. Assessment of MCT-KD adherence will be made by twice weekly unscheduled phone calls by NIH CC Nutrition staff (LAI). There is anticipated accrual of up to two participants admitted at once. MCT oil from Liquigen® (KetoCal) will be given at 25% calculated daily lipid energy expenditure, similar to prior studies (refer to Section 2.3.1 for details of prior studies using MCT oil).

Abbreviated Title: Tolerability and efficacy of ketogenic diet in Parkinson's Disease

Version Date: 04/19/2021

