As per pre-determined scheduled time, subjects will receive monitoring daily on study days 1-7 for 5 minutes using Elite HRV finger monitor and Android application in relaxed waking state in the reclined seated position. Additionally, on study days 1, 7, and week 3 (pre/post intervention), at the time of sessions with rsEEG (see table 2 for testing schedule), trials of Valsalva Maneuver (VM) and deep breathing (DB) will be conducted as follows: VM with coaching to blow into mouthpiece attached to manometer to pressure of 40 mmHg x 15 seconds, and the recording of heart rate cardiovagal gain over the subsequent 1 minute (max RR / min RR interval); average of 3 trials will be used for analysis. DB will occur for 1 minute with 6 cycles per minute, average of 2 trials. Recording for cardiovagal testing will be conducted study day 1, 7, and week 3 via ECG electrodes using Natus Neurology machine (not FDA approved). Analysis will be done using EliteHRV and Biopac Acqknowledge software to extract using artifact removed R-R wave (N-N) intervals SDNN, pNN50, rMSSD, and power spectral analysis (LF, HF, VLF, LF/HF ratio).

Orthostatic vital signs

Orthostatic blood pressure and heart rate will be recorded daily, study days 1-7 and week 3 - supine for 10 minutes or more, then standing immediate followed by standing at 3 minutes.

UPDR parts 1, 2, and 4 will be tested pre vs. post intervention (day 1, week 3). UPDRS-3 will be assessed daily, similar time each day and relation to medications in ON state, with video recording. UPDRS-3 measures to be assessed by board certified neurologist, either directly by AI or rated by blinded rater not affiliated with the study

Abbreviated Title: Tolerability and efficacy of ketogenic diet in Parkinson's Disease

Version Date: 04/19/2021

ON-time, PD symptoms, and keto-induction symptoms will be captured daily via online survey provided / collected to participant daily to check PD / keto symptoms and daily waking hours in the "off" state without effect of dopaminergic medications. Psytoolkit URL:

<https://www.psytoolkit.org/c/3.0.0/survey?s=RQFaX>

Pre vs. post intervention non-motor symptom severity scale (NMSS, Chaudhuri et al 2007, validated by MDS) will be tested for presence/absence of fatigue, pain, urinary disturbance, and other non-motor symptoms (day 1, week 3).

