8.2.1 Clinical Evaluations

Physical examination

Participants will be examined at screening visit by board certified neurologist and movement disorder specialist with focused examination:

general, cardiopulmonary auscultation, neurologic exam with focus on motor or other system disorders (such as sensory, musculoskeletal) related to Parkinson's. There will also be UPDRS and request for video recording. Video record would require separate signed informed consent as per NIH protocol. Video recording is done for research purpose only (quality assessment by averaging scores of in-person rater with a separately blinded video rater).

Examination with requested video recording as per above will be repeated on day of discharge (post-intervention). Examination as per above will also be repeated on day of admission (pre-intervention), without request for video recording unless a significant clinical finding is observed in difference from the screening visit.

Vital signs and Heart rate variability

Vital signs will be done as per routine care in the Metabolic Unit and will also include daily orthostatic check to be done by Metabolic Unit staff or credentialed study investigator. Daily heart rate variability will be performed with pre/post intervention (daily days 1-7 and at week 3) heart rate responses to a) deep breathing at 6 cycles per minute (5 cycles E:I ratio) and difference between average max and min heart rates; and b) Valsalva Ratio (HR max : HR baseline) with Valsalva Maneuver x 15s at 30-40 mmHg (days 1, 7, and week 3).

Radiographic or other imaging assessments

ECG – ECG will be performed at screening or Day 1 of admission (depending on availability), however must be performed prior to diet intervention. A routine ECG will be performed for confirmation of normal cardiopulmonary function. If arrhythmia is detected, Cardiology will be consulted and incorporating their recommendations, decision about remaining or withdrawing from the study based upon the underlying etiology sinus (more likely stay in the study) vs. non-sinus rhythm aberrancy (more likely withdraw from study) as per inclusion/exclusion criteria.

EEG - regional changes in spectral power (theta, alpha, beta) and nonlinear corticocortical synchronization measure via phase lag index (focusing on frontotemporal, parietotemporaloccipital areas

Abbreviated Title: Tolerability and efficacy of ketogenic diet in Parkinson's Disease

Version Date: 04/19/2021

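### UPDRS-III has conflicting scoring rules, and Sections 4.1 and 8.2.1 disagree on day-1 video, so baseline and post-diet scores could come from different methods

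*Combined protocol and SAP*

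**What the plan says.** **Scoring rule.** Three statements are given.

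- Section 4.1, in the text on reducing bias, plans "video rating (aside from muscle tone) of UPDRS-III by the average of AI and another movement disorders specialist outside the study", with "the latter rating scrambled in random assortment with respect to intervention day". The scrambling applies to the outside rater only.
- Section 4.1, in the test descriptions, has a board-certified neurologist score UPDRS-3, "either directly by AI or rated by blinded rater not affiliated with the study".
- Section 8.2.1 gives the purpose of the video as "quality assessment by averaging scores of in-person rater with a separately blinded video rater".

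**Video schedule.** The sentence in Section 4.1 just before the either-rater wording reads "UPDRS-3 will be assessed daily, similar time each day and relation to medications in ON state, with video recording". Section 8.2.1 requests video with the examination at screening and again at discharge, but the examination is "repeated on day of admission (pre-intervention), without request for video recording unless a significant clinical finding is observed" relative to screening. Video needs a separate signed consent.

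**Role of day 1.** The footnote to the schedule in Section 1.3 makes day 1 the first day of admission, and the schedule lists UPDRS part 3 at screening, on every inpatient day and at week 3. Section 4.1 takes day 1 as the pre-diet value for all exploratory outcomes. Section 9.4.3 enters the day-1 value as an ANCOVA covariate. Section 1.1 also plans pre/post comparisons within each group and in all participants, and lists UPDRS among the outcomes.

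**The concern.** A two-rater average and a score from one rater or the other cannot both be the analysed value, and Section 9 does not say which one is. Staff who follow Section 8.2.1 on the admission day would have an in-person score and usually no recording. At discharge they would have a recording and could form the average. The scrambled outside reading cannot include the baseline unless day 1 is filmed.

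This matters most where no control arm exists. In a within-group comparison a change of scoring method coincides exactly with the move from before to after the diet. By week 3 every participant has been on the ketogenic diet, so a reading blind to study day is the main protection against a rater scoring with the timepoint in mind. The either-rater wording allows that protection to be dropped. The protocol itself raises UPDRS reliability in small cohorts as a weakness of previous pilots (Section 2.1) and repeats the point about agreement between and within raters in Section 2.3.3.

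**Working it through.** The plan gives no figure to reproduce. The only power calculation (Section 9.2) is for TUG. The check sets the instructions side by side and then traces a rater difference through the two kinds of analysis.

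**Step 1: what each instruction gives.**

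| Instruction followed | Day 1 | Day 7 | Week 3 |
|---|---|---|---|
| 4.1, average, with daily video | average of two | average of two | average of two if filmed |
| 4.1, either rater | AI or outside rater | AI or outside rater | AI or outside rater |
| 8.2.1 | in-person score only, unless a significant finding | average of two | not addressed |

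Only the first row secures one method at day 1 and day 7. Neither video instruction names week 3 explicitly.

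**Step 2: within-group change.** Let A and B be the mean scores that the AI and the outside rater would give the same performance, and let d = B − A be constant over time. Let D be the true change.

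- Average at both visits: change = D. The offset cancels.
- AI alone at day 1, average afterwards: change = D + [(A + B)/2 − A] = D + d/2.

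The documents give no value for d, so a range is assumed:

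| Assumed d (points) | Shift in change, d/2 (points) |
|---|---|
| 2 | 1 |
| 4 | 2 |
| 6 | 3 |

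The sign depends on which rater scores higher. Muscle tone is not rated from video, so d refers to the remaining items. If the either-rater wording led to the AI alone at day 1 and the outside rater alone afterwards, the shift would be B − A = d, the whole difference.

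**Step 3: randomised day-7 comparison.** The model in Section 9.4.3 can be written Y7 = α + τ·diet + β·Y1 + γ·age + error.

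- A constant offset in Y1 that is the same in both arms changes α and leaves τ alone. The same holds for a constant offset in Y7.
- If the two raters' errors are independent with variance σ² each, a single-rater baseline carries error variance σ², against σ²/2 for the average. The covariate then explains less, and precision falls.
- The protection needs equal scoring by arm. If a fraction p of day-7 scores are averages in one arm and q in the other, and the rest are AI alone, the arm difference picks up (p − q)·d/2. The either-rater wording does not fix p = q.

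**The case against.** A reader might infer that the day-1 score is bound to come from a different method than the later ones. The documents do not support that. Section 4.1 has UPDRS-3 recorded on video daily, and the Section 1.3 schedule includes day 1, so under Section 4.1 the baseline is filmed and can be scored exactly as on day 7. The mismatch arises only if Section 8.2.1 or the either-rater wording is followed.

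Section 8.2.1 is also a thin basis for the UPDRS-3 video schedule. The text sits under physical examination, is silent on days 2 to 6 and week 3, has an exception for a significant finding, and requests a pre-diet video at screening. It can be read as covering the clinical examinations only. Its averaging language broadly agrees with the first rule in Section 4.1, and the either-rater sentence may only describe who is qualified to rate.

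These points reduce the finding to a conflict of instructions, but they do not remove it. The screening video is not the baseline in the ANCOVA, no text gives one section precedence, and the either-rater sentence can be applied as a scoring rule. The rater differences in Step 2 are illustrations, not evidence of size. The stakes are low: Section 3 includes UPDRS for consistency with the existing literature.

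**Conclusion.** The protocol contradicts itself on how UPDRS-III is scored and on whether day 1 is filmed. The baseline could therefore rest on a different method than the day-7 and week-3 scores. If the baseline is the AI alone and later scores are two-rater averages, within-group changes carry half the mean rater difference: 1 to 3 points over the assumed range of 2 to 6 points, with a rater difference that is constant over time.

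A reader might also infer that the randomised diet effect at day 7 is biased. That does not follow. A constant offset common to both arms is absorbed by the intercept, and the main loss is precision, provided both arms are scored alike. The primary feasibility outcome, the TUG comparison and the sample size do not depend on UPDRS-III. This is a minor point, but a baseline that was not filmed cannot be recovered later.

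**What to change.** Reconcile the two statements in Section 4.1 and the one in Section 8.2.1 to a single rule, and refer to it in Section 9.4.3:

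- At day 1, day 7 and week 3, the analysed score is the average of the AI and the outside video rater, with the outside ratings in scrambled day order. State whether the AI scores in person or from the recording, and keep that the same at all three visits.
- Delete the day-1 video exception in Section 8.2.1 and confirm video at week 3.
- Take muscle tone from the in-person rating at all visits.
- For participants who decline video, use the same single-rater score at every visit and never mix it with averaged scores within a participant. Report their number by arm.

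Cost: a text correction and at most one or two extra videos per participant (32 × 1 = 32 to 32 × 2 = 64 in all), read by the outside rater already planned. If recording is already daily as in Section 4.1, day 1 adds nothing.
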